APPENDIX D: EORTC QLQ-MY20 TOOL

ENGLISH

EORTC QLQ – MY20

Patients sometimes report that they have the following symptoms or problems. Please indicate the extent to which you have experienced these symptoms or problems during the past week. Please answer by circling the number that best applies to you.

During the past week:	Not at All	A Little	Quite a Bit	Very Much
31. Have you had bone aches or pain?	1	2	3	4
32. Have you had pain in your back?	1	2	3	4
33. Have you had pain in your hip?	1	2	3	4
34. Have you had pain in your arm or shoulder?	1	2	3	4
35. Have you had pain in your chest?	1	2	3	4
36. If you had pain did it increase with activity?	1	2	3	4
37. Did you feel drowsy?	1	2	3	4
38. Did you feel thirsty?	1	2	3	4
39. Have you felt ill?	1	2	3	4
40. Have you had a dry mouth?	1	2	3	4
41. Have you lost any hair?	1	2	3	4
42. Answer this question only if you lost any hair: Were you upset by the loss of your hair?	1	2	3	4
43. Did you have tingling hands or feet?	1	2	3	4
44. Did you feel restless or agitated?	1	2	3	4
45. Have you had acid indigestion or heartburn?	1	2	3	4
46. Have you had burning or sore eyes?	1	2	3	4

Please turn to next page

ENGLISH

During the past week:	Not at All	A Little	Quite a Bit	Very Much
47. Have you felt physically less attractive as a result of your disease or treatment?	1	2	3	4
48. Have you been thinking about your illness?	1	2	3	4
49. Have you been worried about dying?	1	2	3	4
50. Have you worried about your health in the future?	1	2	3	4

APPENDIX E: ECOG PERFORMANCE STATUS SCALE

ECOG Performance Status Scale		Karnofsky Performance Scale	
Grade	Descriptions	Percent	Description
0	Normal activity. Fully active, able to carry on all pre-disease performance without restriction.	100	Normal, no complaints, no evidence of disease.
		90	Able to carry on normal activity; minor signs or symptoms of disease.
1	Symptoms, but ambulatory. Restricted in physically strenuous activity, but ambulatory and able to carry out work of a light or sedentary nature (e.g., light housework, office work).	80	Normal activity with effort; some signs or symptoms of disease.
		70	Cares for self, unable to carry on normal activity or to do active work.
2	In bed <50% of the time. Ambulatory and capable of all self-care, but unable to carry out any work activities. Up and about more than 50% of waking hours.	60	Requires occasional assistance, but is able to care for most of his/her needs.
		50	Requires considerable assistance and frequent medical care.
3	In bed >50% of the time. Capable of only limited self-care, confined to bed or chair more than 50% of waking hours.	40	Disabled, requires special care and assistance.
		30	Severely disabled, hospitalization indicated. Death not imminent.
4	100% bedridden. Completely disabled. Cannot carry on any self-care. Totally confined to bed or chair.	20	Very sick, hospitalization indicated. Death not imminent.
		10	Moribund, fatal processes progressing rapidly.
5	Dead.	0	Dead.

APPENDIX F: NEW YORK HEART ASSOCIATION FUNCTIONAL CLASSIFICATION SYSTEM

Class	Patient Symptoms
Class I (Mild)	No limitation of physical activity. Ordinary physical activity does not cause undue fatigue, palpitation, or dyspnea (shortness of breath).
Class II (Mild)	Slight limitation of physical activity. Comfortable at rest, but ordinary physical activity results in fatigue, palpitation, or dyspnea.
Class III (Moderate)	Marked limitation of physical activity. Comfortable at rest, but less than ordinary activity causes fatigue, palpitation, or dyspnea.
Class IV (Severe)	Unable to carry out any physical activity without discomfort. Symptoms of cardiac insufficiency at rest. If any physical activity is undertaken, discomfort is increased.

APPENDIX G: LIST OF POTENTIAL DRUG INTERACTIONS

When drugs classified as 'substrates' are co-administered with cabozantinib, there is the potential for higher concentrations of the 'substrate.' When cabozantinib is co-administered with compounds classified as 'inhibitors,' increased plasma concentrations of cabozantinib is the potential outcome. The co-administration of 'inducers' would potentially lower plasma cabozantinib concentrations.

CYP3A4 Substrates

Albuterol	Dihydroergotamine	Isradipine	Quinidine
Alfentanil	Diltiazem	Itraconazole	Rabeprazole
Alprazolam	Disopyramide	Ketamine	Ranolazine
Amiodarone	Docetaxel	Ketoconazole	Repaglinide
Amlodipine	Doxepin	Lansoprazole	Rifabutin
Amprenavir	Doxorubicin	Letrozole	Ritonavir
Aprepitant	Doxycycline	Levonorgestrel	Salmeterol
Aripiprazole	Efavirenz	Lidocaine	Saquinavir
Atazanavir	Eletriptan	Losartan	Sibutramine
Atorvastatin	Enalapril	Lovastatin	Sildenafil
Benzphetamine	Eplerenone	Medroxyprogesterone	Simvastatin
Bisoprolol	Ergoloid mesylates	Mefloquine	Sirolimus
Bortezomib	Ergonovine	Mestranol	Spiramycin
Bosentan	Ergotamine	Methadone	Sufentanil
Bromazepam	Erythromycin	Methylergonovine	Sunitinib
Bromocriptine	Escitalopram	Methysergide	Tacrolimus
Budesonide	Estradiol	Miconazole	Tamoxifen
Buprenorphine	Estrogens, conj., synthetic	Midazolam	Tamsulosin
Buspirone	Estrogens, conj., equine	Miglustat	Telithromycin
Busulfan	Estrogens, conj., esterified	Mirtazapine	Teniposide
Carbamazepine	Estrone	Modafinil	Tetracycline
Cerivastatin	Estrropipate	Montelukast	Theophylline
Chlordiazepoxide	Ethinyl estradiol	Moricizine	Tiagabine
Chloroquine	Ethosuximide	Nateglinide	Ticlopidine
Chlorpheniramine	Etoposide	Nefazodone	Tipranavir
Cilostazol	Exemestane	Neifinavir	Tolterodine
Cisapride	Felbamate	Nevirapine	Toremifene
Citalopram	Felodipine	Nicardipine	Trazodone
Clarithromycin	Fentanyl	Nifedipine	Triazolam
Clobazam	Flurazepam	Nimodipine	Trimethoprim
Clonazepam	Flutamide	Nisoldipine	Trimipramine
Clorazepate	Fluticasone	Norethindrone	Troleandomycin
Cocaine	Fosamprenavir	Norgestrel	Vardenafil
Colchicine	Gefitinib	Ondansetron	Venlafaxine
Conivaptan	Haloperidol	Paclitaxel	Verapamil
Cyclophosphamide	Ifosfamide	Pergolide	Vinblastine
Cyclosporine	Imatinib	Phencyclidine	Vincristine
Dantrolene	Indinavir	Pimozide	Vinorelbine
Dapsone	Irinotecan	Pipotiazine	Zolpidem
Dasatinib (1)	Isosorbide	Primaquine	Zonisamide
Delavirdine	Isosorbide dinitrate	Progesterone	Zopiclone
Diazepam	Isosorbide mononitrate	Quetiapine	

CYP3A4 Inhibitors

Strong inhibitors:	Moderate inhibitors:	Weak inhibitors:	All other inhibitors:
indinavir nelfinavir ritonavir clarithromycin itraconazole ketoconazole nefazodone saquinavir suboxone telithromycin cobicistat boceprevir mibefradil telaprevir troleandomycin posaconazole	aprepitant amprenavir amiodarone atazanavir ciprofloxacin crizotinib darunavir/ritonavir dronedarone erythromycin diltiazem fluconazole grapefruit juice Seville orange juice verapamil voriconazole imatinib	cimetidine fluvoxamine	chloramphenicol delavirdine diethyl-dithiocarbamate gestodene mifepristone norfloxacin norfluoxetine star fruit

CYP3A4 Inducers

Aminoglutethimide Carbamazepine Fosphenytoin Nafcillin	Nevirapine Oxcarbazepine Pentobarbital Phenobarbital	Phenytoin Primidone Rifabutin Rifampin	Rifapentine St. John's wort (3)
---	---	---	------------------------------------

When drugs classified as 'substrates' are co-administered with cabozantinib, there is the potential for higher concentrations of the 'substrate'. When cabozantinib is co-administered with compounds classified as 'inhibitors', increased plasma concentrations of cabozantinib is the potential outcome. The co-administration of 'inducers' would potentially lower plasma cabozantinib concentrations.

Note: Adapted from Cytochrome P450 Enzymes: Substrates, Inhibitors, and Inducers. In: Lacy CF, Armstrong LL, Goldman MP, Lance LL eds. Drug Information Handbook 15TH ed. Hudson, OH; LexiComp Inc. 2007: 1899-1912.

Only major substrates and effective inducers are listed.

Additional information for drug interactions with cytochrome P450 isoenzymes can be found at <http://medicine.iupui.edu/flockhart/>.

- (1) Wang *et al.* (2004). *Clin Pharmacol Ther.* 75:191-197
- (2) Malhotra *et al.* (2001). *Clin Pharmacol Ther.* 69:14-23.
- (3) Mathijssen *et al.* (2002). *J Natl Cancer Inst.* 94:1247-1249.
- (4) Frye *et al.* (2004). *Clin Pharmacol Ther.* 76:323-329.

APPENDIX H: STUDY MEDICATION DIARY

CYCLE _____ Date _____

Study ID: _____

Your prescribed dose of cabozantinib is _____. Number of Pills Dispensed: _____

- If you miss a dose please add the comment "missed dose" on the corresponding date. Dose should not be replaced.
- If your Study Doctor has asked you to change your dose, please add the new dosage on the corresponding date.
- Return all study drug bottles, any unused drug and completed diaries to the Study Coordinators at the study site.

Cabozantinib tablets should be taken by mouth, at least 2 hours before and at least 1 hour after eating. Tablets should be taken with water and swallowed whole.

You are to take your study medication as follows:

# of Pills	# of time(s) per day	Duration: days/weeks/months	Special instruction

Month

Sunday	Monday	Tuesday	Wednesday	Thursday	Friday	Saturday

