2.2.2 CLINICAL PHARMACOKINETICS

A population pharmacokinetic analysis of cabozantinib (COMETRIQ) was performed using data collected from 289 patients with solid tumors including MTC following oral administration of 140 mg daily doses. The predicted effective half-life is approximately 55 hours, the oral volume of distribution (V/F) is approximately 349 L, and the clearance (CL/F) at steady-state is estimated to be 4.4 L/hr³².

Absorption and Distribution:

Following oral administration of cabozantinib, median time to peak cabozantinib plasma concentrations (T_{max}) ranged from 2 to 5 hours post-dose. Repeat daily dosing of cabozantinib at 140 mg for 19 days resulted in 4- to 5-fold mean cabozantinib accumulation (based on AUC) compared to a single dose administration; steady state was achieved by Day 15. Cabozantinib is highly protein bound in human plasma (≥ 99.7%). A high-fat meal increased C_{max} and AUC values by 41% and 57%, respectively relative to fasted conditions in healthy subjects administered a single 140 mg oral cabozantinib dose³².

Metabolism and Elimination:

Cabozantinib is a substrate of CYP3A4 in vitro. Inhibition of CYP3A4 reduced the formation of the XL184 N-oxide metabolite by >80%. Inhibition of CYP2C9 had a minimal effect on cabozantinib metabolite formation (i.e., a <20% reduction). Inhibition of CYP1A2, CYP2A6, CYP2B6, CYP2C8, CYP2C19, CYP2D6 and CYP2E1 had no effect on cabozantinib metabolite formation. Within a 48-day collection period after a single dose of 14C-cabozantinib in healthy subjects, approximately 81% of the total administered radioactivity was recovered with 54% in feces and 27% in urine³².

As such, because there is a potential for interaction of cabozantinib with other concomitantly administered drugs through the cytochrome P450 system, the case report form must capture the concurrent use of all other drugs, over-the-counter medications, or alternative therapies. The Principal Investigator should be alerted if the patient is taking any agent known to affect or with the potential to affect selected CYP450 isoenzymes.

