5. TREATMENT PLAN

5.1 AGENT ADMINISTRATION

The recommended starting daily dose of cabozantinib is 20 mg (one 20-mg capsules). It will not be administered with food. Patients will be instructed not to eat for at least 2 hours before and at least 1 hour after taking cabozantinib. Capsules will be swallowed as whole and will not be opened. Patients will be instructed to not take a missed dose within 12 hours of the next dose. cabozantinib will not be ingested with grapefruit, grapefruit juice or nutritional supplements that are known to inhibit cytochrome P45.

Treatment will be administered on an outpatient basis. Reported adverse events and potential risks are described in Section 9. Appropriate dose modifications are described in Section 5.7. No investigational or commercial agents or therapies other than those described below may be administered with the intent to treat the patient's malignancy.

To assess compliance with treatment, all patients will be requested to maintain a medication diary of each dose of medication. This medication diary will be returned to the research staff at the end of each cycle of therapy. A sample patient study medication diary is provided in Appendix H.

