5.1.1 Cabozantinib

Cabozantinib tablets should be administered by mouth (PO) daily (one 20-mg capsules for the initial testing dose). Tablets should be taken with water and swallowed whole, and missed or vomited dose should not be replaced. The patient should be instructed to take the next scheduled dose at the regularly scheduled time. Patients will receive cabozantinib daily continuously during entire 28-day treatment cycle (Days 1-28 on therapy).

Refer to Section 8.2.4 for further details on administrations of other study drugs, carfilzomib and dexamethasone.

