Cabozantinib must be taken on an empty stomach. Patients taking cabozantinib tablets should be instructed not to eat for at least 2 hours before and at least 1 hour after taking cabozantinib. Subjects should be instructed to take their cabozantinib dose at approximately the same time every day. If a subject misses a dose, the dose may be taken later only if it is within 12 hours of when the missed dose should have been taken. The missed dose should not be made up if it is within 12 hours of the next scheduled dose.

Cabozantinib tablets should be swallowed whole with at least 8 ounces of water. The tablets should be swallowed whole with water, and cannot be crushed or broken. Grapefruit, grapefruit juice, Seville oranges and their products should be avoided by subjects taking cabozantinib.

In all subjects, dose reductions and delays to manage toxicity are allowed under the guidelines in Section 5.7.

8.1.5 Potential Drug Interaction:

Cabozantinib is metabolized via a drug metabolizing enzyme system associated with cytochrome P450 (CYP3A4). Interactions with drugs metabolized via the same enzyme system are possible. Drugs which inhibit CYP3A4 may markedly increase the plasma concentration of cabozantinib.

Drugs and substances which inhibit CYP3A4 may increase the plasma concentrations of cabozantinib.

Please refer to the drug interaction tables at the following websites for lists of substrates, inducers, and inhibitors of selected CYP450 isozyme pathways:

<http://medicine.iupui.edu/flockhart/table.htm>

<http://www.fda.gov/Drugs/DevelopmentApprovalProcess/DevelopmentResources/DrugInteractionsLabeling/ucm080499.htm>

Protein Binding: Cabozantinib is highly bound ($\geq 99.7\%$) to human plasma proteins. Therefore, highly protein bound drugs should be used with caution with cabozantinib because there is a potential displacement interaction that could increase free concentrations of cabozantinib and/or a co-administered highly protein-bound drug (and a corresponding increase in pharmacologic effect).

8.1.6 Other Interactions:

Food may increase exposure levels of cabozantinib by 57%, fasting recommendations should be followed. Subjects should fast (with the exception of water) for at least 2 hours after eating the evening meal before taking their dose of cabozantinib. After the 2-hour fast and before going to bed, subjects are to take cabozantinib with a full glass of water (minimum of 8 oz or 240 mL) with no more food intake for one hour post-dose.

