10.2 Analytic Plan

For the phase I study, we will examine three doses, with the first cohort assigned to 20 mg orally daily dose. The MTD will be defined via the 3+3 algorithm, i.e. as the dose level below the one at which 1/3 or 2/6 patients experience DLTs. At the completion of the phase II section, the ORR will be estimated as the proportion of patients with ORR and will be accompanied by a 95% confidence interval.

All observed toxicities will be tabulated by type and grade. All remaining secondary aims will be assessed with descriptive statistics and graphical displays to evaluate changes in outlined serum and bone marrow markers between pre- and post-treatment. A paired t-test will be used to examine differences pre- and post-treatment.

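### The patient diary reverses the two fasting intervals, so it permits a dose 1 to 2 hours after a meal that the protocol forbids; the missed-dose rules also disagree

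*Combined protocol and SAP*

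**What the plan says.** **Fasting.** Section 5.1 sets the rule relative to the dose: "Patients will be instructed not to eat for at least 2 hours before and at least 1 hour after taking cabozantinib". Section 8.1.4 repeats it. Section 8.1.6 turns it into a bedtime routine: "Subjects should fast (with the exception of water) for at least 2 hours after eating the evening meal before taking their dose of cabozantinib", followed by one hour without food.

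Appendix H, the page the patient holds, says: "Cabozantinib tablets should be taken by mouth, at least 2 hours before and at least 1 hour after eating". Section 5.1 makes the diary the compliance record: "all patients will be requested to maintain a medication diary of each dose of medication".

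**Reason for the fast.** Section 2.2.2 reports that a high-fat meal raised Cmax and "AUC values by 41% and 57%, respectively relative to fasted conditions in healthy subjects administered a single 140 mg oral cabozantinib dose". Section 8.1.6 cites the 57% as the reason to fast.

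**Missed doses.** Section 5.1.1 says a "missed or vomited dose should not be replaced", and the diary agrees: "Dose should not be replaced". Section 8.1.4 lets a missed dose be taken up to 12 hours late. Section 5.1 bars it only within 12 hours of the next dose.

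**Use of the phase I data.** Section 10.2 defines the MTD "as the dose level below the one at which 1/3 or 2/6 patients experience DLTs", and section 5.7 counts only cycle 1 events as DLTs.

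**The concern.** The diary keeps the numbers 2 and 1 in the protocol's order but moves the reference point from the tablet to the meal, which swaps the intervals. The interval it halves is the one before the dose. Under the bedtime routine of section 8.1.6 that is the interval that matters most, since a patient going to bed gains little from an extra hour without food afterwards.

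The breach would also leave no trace. The daily diary cells record the number of pills and the time, not meals, so a patient who follows the printed instruction exactly would show a clean compliance record while departing from the protocol.

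In phase I, escalation turns on one or two patients per cohort. The dosing instruction patients receive should therefore be the one the protocol specifies. The missed-dose conflict is a smaller, separate matter: the same late dose is compliant under one section and a deviation under another.

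**Working it through.** The plan gives no figure of its own to reproduce here. The check is a comparison of the instructions, followed by a bound on exposure.

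**1. Fasting rules expressed as allowed dose times**

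| Source | Earliest dose after the last meal | Earliest food after the dose | Total food-free window |
|---|---|---|---|
| Sections 5.1, 8.1.4, 8.1.6 | 2 h | 1 h | 3 h |
| Appendix H diary | 1 h | 2 h | 3 h |

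The window has the same length but a different position. The diary permits a dose 1 to 2 hours after a meal, which all three sections forbid. It also forbids food 1 to 2 hours after the dose, which they allow.

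**2. Bound on the exposure effect**

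Inputs from section 2.2.2: +57% AUC and +41% Cmax, for a high-fat meal against fasting, single 140 mg dose, healthy subjects. Dose levels from section 5.7: 20, 40 and 60 mg.

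Assumptions, none of them in the documents: exposure is proportional to dose; the single-dose effect carries over to steady state; a fraction *f* of the full effect applies to a dose 1 to 2 hours after a meal; this happens every day.

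Fasted-equivalent dose on AUC = dose × (1 + 0.57 × *f*).

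| *f* | Multiplier | 20 mg acts like | 40 mg acts like |
|---|---|---|---|
| 25% | 1.1425 | 22.9 mg | 45.7 mg |
| 50% | 1.285 | 25.7 mg | 51.4 mg |
| 100% | 1.57 | 31.4 mg | 62.8 mg |

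On Cmax at full effect: 20 × 1.41 = 28.2 mg and 40 × 1.41 = 56.4 mg.

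- **20 to 40 mg:** this needs a 100% increase. The maximum is 57%, so it is not reached.
- **40 to 60 mg on AUC:** this needs a 50% increase, so *f* = 50/57 = 87.7%. If instead the full effect applied on only some days, weighted equally, 0.877 × 28 = 24.6, so 25 of the 28 days.
- **40 to 60 mg on Cmax:** not reached (56.4 mg).

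**3. Missed doses**

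| Source | Rule |
|---|---|
| Section 5.1.1 and diary | Never replaced |
| Section 8.1.4 | May be taken up to 12 h late |
| Section 5.1 | Not within 12 h of the next dose; earlier replacement implied |

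With once-daily dosing, 24 − 12 = 12, so the limits in sections 5.1 and 8.1.4 agree with each other. The conflict is between them and section 5.1.1 with the diary. One unreplaced dose lowers the cycle's total dose by 1/28 = 3.6%.

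**The case against.** The diary is not the patient's only instruction. Section 5.1 says patients will be told the correct fast, section 8.1.6 gives a concrete evening routine, Appendix H is described as a sample, and the form has a field for special instructions. A patient following section 8.1.6 would not dose in the disputed window. This makes daily dosing in that window a possibility rather than the expected behaviour, but it does not remove the conflict: a template with the wrong sentence is likely to be issued with it, and correct counselling leaves the patient holding a page that contradicts it.

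The exposure effect is unknown and probably below the full figure, which comes from a high-fat meal. That stands, and it is why the calculation is only a range. The 25-of-28-days figure also weights days equally, although section 2.2.2 gives a half-life of about 55 hours and steady state by Day 15, so it is only a rough guide.

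The link to the MTD is general: any source of variability can tip a 3+3 decision. That also stands. No sample size, error rate or analysis rule is affected.

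Finally, section 5.1 contains only a prohibition on late doses, and permission is implied. The explicit missed-dose conflict is section 8.1.4 against section 5.1.1 and the diary.

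**Conclusion.** The concern holds. The diary's fasting instruction is wrong as written: it allows a dose 1 to 2 hours after a meal, contrary to three sections of the protocol, for a drug whose AUC the protocol says can rise by 57% with food. This conclusion rests on the text alone.

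The size of the effect rests on assumption. Within the range shown, 20 mg stays well short of the next dose level, and 40 mg reaches 60 mg only on AUC and only near the full high-fat-meal effect. The documents do not establish that the error would produce a DLT or change the MTD. The case for correcting it is that the error is certain, is in the patient's hands, cannot be detected from the diary and is cheap to remove.

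The missed-dose conflict also holds. It does not raise exposure above plan; its consequence is inconsistent compliance records.

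**What to change.** Rewrite the diary sentence so that it is timed from the tablet and matches section 5.1: no food in the two hours before the dose or in the hour after it. Reissue the page.

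Separately, adopt one missed-dose rule in sections 5.1, 5.1.1 and 8.1.4 and in the diary. One option is to allow a late dose only if it is not within 12 hours of the next one, and not to replace vomited doses. The choice of rule belongs to the clinical team.

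The cost is one corrected diary page, small text edits and an IRB submission. Sample size and timelines are unaffected.

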# of pills _____						
Time ____ am/pm						
